7.7 Healthcare Resource Utilization

Healthcare resource utilization (HCRU) information is collected up to safety follow up visit 1 (100 days after last dose of study treatment), and will be summarized by treatment group. The HCRU summary includes:

- Number of hospitalizations per patient (0, 1, 2, > 2) for overall and by hospitalization ward (general ward, intensive care ward, rehabilitation ward, hospice ward, other ward)

- Number of hospitalizations per person-year
 - Numerator is number of hospitalizations from all patients in the analysis population.
 - Denominator is the sum of $\{\min[(\text{last dose date} + 100 \text{ days}), \text{last known alive date}] - \text{first dose date} + 1\}$ across all patients in the analysis population /365.25.
- Number of days in each specific hospitalization ward per person-year. Specific hospitalization ward includes general ward, intensive care ward, rehabilitation ward, hospice ward, other ward, and overall.
 - Numerator is sum of number of days in each specific hospitalization ward from all patients in the analysis population.
 - Denominator is the sum of $\{\min[(\text{last dose date} + 100 \text{ days}), \text{last known alive date}] - \text{first dose date} + 1\}$ across all patients in the analysis population /365.25.

A by-patient listing of HCRU data will also be provided.

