EQ-5D-3L	X		X	X	X	Patients should complete the assessment at the start of the clinic visit, prior to dosing and scheduled activities.
FKSI-19	X		X	X	X	
PRO-CTCAE	X		X	X	X	Completed on Days 1 and 22 of every cycle through Cycle 4, and then on Day 1 of the following cycles. See Section 7.6 for further details.

Abbreviations used in this table appear on the final page of [Table 4](#).

Table 3: On-Treatment Schedule of Events for Arm B (Contd)

Procedure ^a	Arm B Cabozantinib 60 mg PO once daily (continuously) OR Sunitinib 50 mg PO once daily (4 weeks on treatment, followed by 2 weeks off treatment) Cycle = 6 Weeks					Notes
	Cycle 1			Cycle 2 and subsequent on-treatment visits		
	Day 1	Day 8 (-1 day)	Day 22 (± 3 days)	Day 1 (± 3 days)	Day 22 (± 3 days)	
Health Care Resource Utilization	X		X	X	X	Site staff will collect the health care resource utilization data at each visit using the CRF.

a. Assessments and visits that occur outside of protocol-specified windows (e.g., for holidays, travel issues, insurance issues) may be acceptable on a case-by-case basis after review by the Medical Monitor.

Abbreviations used in this table appear on the final page of [Table 4](#).

Table 4: Long-Term Follow-Up Schedule of Events

Procedure ^a	Safety Follow-Up Visit 1 ^b	Safety Follow-Up Visit 2 ^b	Survival Follow-Up ^c Every 12 Weeks (± 14 days)	Notes ^d
Safety Assessments				
Vital Signs	X	X		Blood pressure, heart rate, temperature Weight
AE and SAE Assessments	X	X	X	All AEs will be documented until 100 days after the last dose of all study drug(s). SAEs to be collected after the 100-day safety visit if the SAE is deemed to be related or residual toxicities are persisting. Patients will be followed for drug-related toxicities until these toxicities resolve, return to baseline, or are deemed irreversible.
Karnofsky Performance Status	X	X		See Appendix 2 .
Review of Subsequent Medications and Anticancer Therapy	X	X	X	In Survival Follow-up, subsequent anticancer treatment only. Additional subsequent anticancer therapy details such as regimen, setting of the regimen, line of therapy, start date and end date of each regimen, best response to the regimen, and date of progression to subsequent anticancer therapies will be collected.
Laboratory Tests				
Pregnancy Test (WOCBP only)	X	X		Patients (WOCBP) will continue to follow instructions for methods of contraception through 5 months post treatment completion.

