Brain Imaging	
 Patients with a history of brain metastasis or neurological symptoms should have MRI with and without contrast. See Section 7.2 if patient has contraindications to contrast MRI. Brain imaging assessments should be performed on same schedule as body tumor assessments, or as clinically indicated Tumor assessments will continue until both BICR and Investigator’s assessments of tumor images have determined progression. Patients who are receiving study treatment beyond progression should continue scans until the criteria for treatment discontinuation are met and BICR-assessed progression has occurred. Tumor assessments are no longer required if subsequent anticancer therapy is started, even if the patient has not yet progressed. Use same imaging method as was used at screening. 			All study treatment decisions will be based on the Investigator’s assessment of tumor images. See Section 7.0 for further details.
Survival Status			X	Survival Follow-up can be administered in person or by telephone, if needed.
Health Outcomes Assessments				
EQ-5D-3L	X			See Section 7.6 for further details.
FKSI-19	X			
PRO-CTCAE	X			
Health Care Resource Utilization	X			Study site staff should collect health care resource utilization data using the CRF.

AE = adverse event; BICR = blinded independent central review; CT = computed tomography; CRF = case report form; CVA = cerebrovascular accident; ECG = electrocardiogram; eCRF = electronic case report form; EQ-5D-3L = 3-level version of the EuroQol Group’s EQ-5D; FKSI-19 = Functional Assessment of Cancer Therapy (FACT) Symptom Index for Kidney Cancer; hCG = human chorionic gonadotropin; IMDC = International Metastatic RCC Database Consortium; IV = intravenous(ly); MRI = magnetic resonance imaging;

MUGA = multigated acquisition; PK = pharmacokinetic(s); PO = orally; PRO-CTCAE = Patient-Reported Outcomes version of the Common Terminology Criteria for Adverse Events; q3w = every 3 weeks; RCC = renal cell carcinoma; SAE = serious adverse event; TIA = transient ischemic attack; UPCR = urine protein creatinine ratio; VW = vital signs and weight only; WOCBP = women of childbearing potential

- a. Assessments and visits that occur outside of protocol-specified windows (e.g., for holidays, travel issues, insurance issues) may be acceptable on a case-by-case basis after review by the Medical Monitor.

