- b. Patients must be followed for 100 days after the last dose of study treatment. Safety Follow-Up Visit 1 should occur 30 (\pm 7) days from the last dose of all study drug(s), or at the time of permanent treatment discontinuation if discontinuation is after the Safety Follow-Up Visit 1 window. Safety Follow-Up Visit 2 occurs 100 (\pm 7) days from the last dose of all study drug(s). Safety Follow-up Visits should occur regardless of initiation of subsequent anticancer therapy. Both Safety Follow-up Visits should be conducted in person.
- c. Survival Follow-Up to occur every 12 weeks (\pm 14 days) following the Safety Follow-Up Visit 2. Survival Follow-Up may be conducted in person or by telephone. The Sponsor may request that survival data be collected on all treated patients outside of the 3-month specified window. At the time of this request, each patient will be contacted to determine their survival status unless the patient has withdrawn consent for all contact. Information about subsequent anticancer therapy will also be collected during these contacts.
- d. Some of the assessments referred to in this section may not be captured as data in the eCRF. They are intended to be used for safety monitoring purposes by the treating physician. Additional testing or assessments may be performed as clinically necessary or where required by institutional or local regulations.

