5.6.1 Safety Follow Up

- Safety Follow-up Visit 1 should occur 30 (± 7) days from the last dose of all study drug, or at the time of permanent treatment discontinuation if discontinuation is after the Safety Follow Up Visit 1 window.
- Safety Follow-up Visit 2 occurs 100 (± 7) days from the last dose of all study drug. Safety follow-up visits should occur regardless of initiation of subsequent anticancer therapy.
- Both Safety Follow-Up Visits should be conducted in person.
- Per clinical judgment, the patient may come in earlier for additional follow up.

- Patients will also be followed for safety until resolution or permanent sequelae of all toxicities attributable to study drugs (NKTR-214 and/or nivolumab or TKI) as outlined in Sections 8.5 and 8.8.
- For AE and SAE reporting periods, please refer to Sections 8.5 and 8.7.

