5.11 Medical Resource Utilization and Health Economics

Health care resource utilization data will be collected for all randomized patients using an internal case report form (CRF) developed for use in previous trials. The form, which is completed by study staff, records information about hospital admissions, including number of

days spent in various wards and discharge diagnosis, as well as non-protocol specified visits related to study therapy, including date of visit, reason for visit, and type of visit. The health care resource utilization data will be used to support subsequent economic evaluations.

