PRO-CTCAE	
Summary statistics for PRO-CTCAE at each assessment point and per item will be summarized for each treatment group. The mean change from baseline will also be reported at each post baseline assessment point.

HCRU	
Summary statistics for HCRU at each assessment point will be summarized for each treatment group.

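### SAP 7.7 dates Safety Follow-Up Visit 1 at 100 days and runs HCRU person-time to day 100; the protocol puts that visit at 30 days and schedules no HCRU after it, so the rates are understated if collection ended there

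*SAP*

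**What the plan says.** **SAP 7.7.** "Healthcare resource utilization (HCRU) information is collected up to safety follow up visit 1 (100 days after last dose of study treatment"). It plans two rates, hospitalisations per person-year and days in each ward type per person-year. Both use the same denominator. Each patient contributes the days from first dose to the earlier of last dose + 100 days and the last known alive date; the sum is divided by 365.25. The numerators are totals over all patients, with no date window.

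**Protocol 1.2, Table 4, footnote b.** "Safety Follow-Up Visit 1 should occur 30" (±7) days after last dose, "or at the time of permanent treatment discontinuation if discontinuation is after the Safety Follow-Up Visit 1 window".

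**Protocol 5.6.1.** The same timing for Visit 1, and "Safety Follow-up Visit 2 occurs 100" (±7) days after last dose.

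**Protocol 1.2, Table 4, HCRU row.** Marked under Visit 1; the Visit 2 and Survival Follow-Up cells are blank. The note reads "Study site staff should collect health care resource utilization data using the CRF".

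**Links between HCRU and visits.** The Arm B on-treatment schedule (Table 3) says "Site staff will collect the health care resource utilization data at each visit using the CRF". Protocol 9.5 says "Summary statistics for HCRU at each assessment point will be summarized for each treatment group". Protocol 5.11 describes a form that records hospital admissions, including "days spent in various wards and discharge diagnosis", and gives no end date for collection.

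**The concern.** The 100-day figure is more than a description. It fixes the end of person-time in two formulas. A rate per person-year is valid only if events are captured over the same period that is counted as time at risk. The protocol schedules no HCRU collection after Visit 1, at about day 30, while the SAP counts time to day 100. If the form stopped at Visit 1, the last 70 days or so add to the denominator and almost nothing to the numerator.

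What is at stake is limited. SAP 7.7 tests no hypothesis, and the count of hospitalisations per patient (0, 1, 2, more than 2) does not use the denominator. Protocol 5.11 does say that the data will support later economic evaluations, where a rate per person-year is a natural input.

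**Working it through.** **1. Which visit is at 100 days?** SAP 7.7 says Visit 1. Protocol Table 4 (footnote b) and Section 5.6.1 say Visit 2. The SAP's timing for Visit 1 cannot be reproduced from the protocol.

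**2. Gap for one patient off treatment and alive at day 100, if collection follows Table 4.** With Visit 1 at day *v* after last dose, uncollected person-time = 100 − *v*.
- *v* = 30: 100 − 30 = 70 days
- *v* = 37: 100 − 37 = 63 days
- *v* = 23: 100 − 23 = 77 days

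**3. Who adds less, or nothing.**
- Late Visit 1 (the footnote b exception): Protocol 5.14.1.1 generally requires discontinuation after a dosing delay of more than 8 weeks. A Visit 1 at day 56 would leave 100 − 56 = 44 days.
- Death before Visit 1: no excess, because SAP 6.6 sets the last known alive date to the death date. Death or last contact between Visit 1 and day 100 gives a smaller gap.
- On treatment at data cutoff: no post-treatment excess, because SAP 6.6 caps the last known alive date at cutoff.
- Ward days only: the gap matters less if an admission open at Visit 1 is recorded to discharge.

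**4. Illustration for one patient.** Let *D* = days on treatment (last dose − first dose + 1). SAP person-time is *D* + 100; time to Visit 1 is *D* + *v*. With a constant event rate and nothing recorded after Visit 1, the reported rate divided by the matched rate is (*D* + *v*)/(*D* + 100). The documents give no expected treatment durations, so *D* is assumed.

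| *D* (assumed) | *v* = 30 | *v* = 23 to 37 |
|---|---|---|
| 180 | 210/280 = 0.75 | 0.73 to 0.78 |
| 365 | 395/465 = 0.85 | 0.83 to 0.86 |
| 730 | 760/830 = 0.92 | 0.91 to 0.92 |

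With Visit 1 at day 56 the ratio is 236/280 = 0.84 at *D* = 180 and 421/465 = 0.91 at *D* = 365. These are single-patient ratios. SAP 7.7 pools events and person-time over all patients, including those in step 3 who add little or no excess. Reading a pooled figure off this table would need the distributions of treatment duration, follow-up and Visit 1 dates, which the documents do not give.

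**The case against.** The best defence is that SAP 7.7 agrees with itself. It states collection to 100 days and counts person-time to 100 days, so the only slip may be the visit number. The figure appears three times in the section and is a standard window in this trial: adverse events (Protocol 8.2, 8.5), serious adverse events (8.7), the extended treatment-emergent period (SAP 6.6) and concomitant medications (SAP 6.4, 7.4.1). Inpatient hospitalisation is itself a seriousness criterion (Protocol 8.6), so sites ascertain admissions to day 100.

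This stands as a live alternative. It means that a mismatch between numerator and denominator is not established, only a conflict between documents. It does not close the point. SAP 7.7 does not name serious adverse event reports as an HCRU source, and Table 4 leaves the HCRU cell at Visit 2 blank. On the label-error reading the rates stand, but the SAP visit label and the Table 4 row still need correcting.

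A reader might go further and infer that the reported rates are too low by the single-patient percentages above, or that the comparison between arms is distorted because treatment durations differ. The documents support neither inference. They give no CRF end date, and the ratios rest on assumed durations and are not pooled. No size or direction by arm can be derived.

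**Conclusion.** The conflict between SAP 7.7 and the protocol is certain. Its effect on the rates is conditional. If HCRU collection ended at Visit 1 as Table 4 schedules, each patient off treatment and alive at day 100 contributes 63 to 77 days of person-time without scheduled collection (less with a late Visit 1), and both rates per person-year are understated by an amount that cannot be determined from the documents. If the form ran to day 100, the rates are sound and only the SAP label and the Table 4 row are wrong. No primary or key secondary analysis is touched. A correction is still worth making before the analysis, because following the protocol schedule and the SAP formula as written gives the wrong denominator.

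**What to change.** First check the collection period of the HCRU form.

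**If collection ended at Visit 1:**
- End person-time in both denominators at each patient's last actual HCRU collection date, which is the Visit 1 date where that visit took place, and never later than the last known alive date or data cutoff.
- Count hospitalisations and ward days in that same window, and say how ward days of an admission still open at its end are treated.
- Correct the visit timing in SAP 7.7.

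A fixed cut at last dose + 30 days is not a substitute. For a patient who missed Visit 1 it would credit time with no collection. For a patient in a long dose delay at cutoff it would discard any time with HCRU collection after that point.

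**If the form captured admissions to day 100:** keep the denominators, change the SAP label to Visit 2, and reconcile the HCRU row of protocol Table 4 with it.

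**Cost.** The first branch needs a CRF check, one end-of-window definition used in two formulas and a text correction, with no new data. The second needs no reprogramming, but Table 4 is protocol text, and under Protocol 12.1 amendments go through ethics review. It could reasonably be carried with the next amendment.

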7.8 Immunogenicity

7.8.1 Immunogenicity Measurements and Endpoints

The immunogenicity analysis will be performed separately for anti-NKTR-214/anti-PEG, anti-IL-2 and anti-nivolumab antibodies. The data will be summarized for anti-NKTR-214/anti-PEG, anti-IL-2 and anti-nivolumab antibodies and will be reported by both sample and patient status.

For sample status, baseline samples will be classified as:

- baseline ADA-positive, if ADA is detected in the immunogenicity sample collected before initiation of the treatment and
- baseline ADA-negative, if ADA is not detected in the immunogenicity sample collected before initiation of the treatment.

ADA samples will be classified as positive if after initiation of the treatment, the ADA is detected (positive seroconversion) in a sample from a patient who was baseline ADA-negative, or if there is at least 4-fold or greater (\geq) increase in ADA titer in comparison to the baseline positive titer. Samples confirmed to be positive for anti-NKTR-214/anti-PEG, anti-IL-2 antibodies will be tested for neutralizing activity for IL-2 using a validated cell-based assay. Anti-nivolumab antibodies positive samples will also be tested for neutralizing activity for nivolumab using a validated cell-based assay. ADA-positive samples with neutralizing activity will be classified as neutralizing positive.

For patient status, immunogenicity will be reported by summarizing the number and percentage of ADA-positive patients and ADA-negative patients at baseline and after drug administration with positive status of anti-NKTR-214, anti-PEG, anti-IL-2, and anti-nivolumab ADA. In the

immunogenicity evaluable population, the patients will be classified as treatment-induced ADA-positive if they were ADA-negative at baseline and became ADA-positive at any time after starting the treatment, or if they were ADA-positive at baseline and had a post-baseline ADA-positive titer that was at least 4-fold or greater (\geq) than baseline positive titer (also known as Treatment-boosted). The patients with an ADA-positive sample at 2 or more consecutive time points, where the first and last ADA-positive samples are at least 16 weeks apart will be classified as persistent positive. Patients that are not persistent positive but have an ADA-positive sample at the last sampling time point will be classified as not persistent last-sample positive. Non persistent positive patients with an ADA-negative sample at the last sampling time point will be classified as transiently positive or other positive. Patients with at least 1 ADA-positive sample with neutralizing activity will be classified as neutralizing positive. All other ADA-evaluable patients are considered as treatment-emergent ADA negative.

All ADA-positive patients will be included in the ADA titer kinetics analysis. Summary statistics of patient-level ADA titers using the maximum titer value within an ADA-positive patient will be presented for baseline ADA-negative patients and baseline ADA-positive patients. The median, interquartile range, and range of the maximum titers will be reported. For ADA-positive patients with baseline ADA-positive sample, the median and interquartile range of the fold increase from baseline in titer (ratio of maximum post-baseline titer to baseline titer) will also be reported. For sample-level ADA titers, boxplots of ADA titers at each assessment timepoint will be provided, as appropriate, to demonstrate whether the ADA levels tend to change over time during the treatment, along with ADA incidence at each assessment timepoint.

Analyses of ADA kinetics, including the onset and duration of ADA, will include only those ADA-positive patients that were ADA-negative at baseline. ADA-positive patients with baseline ADA-positive sample and an increased titer post-baseline will be excluded since this type of immune response differs mechanistically.

Onset of ADA refers to the time period between the first dose of the treatment and the first instance of ADA detection. The median, interquartile range, and range of time to ADA development will be provided. The median and range of the number of treatment doses to before and after the first detection of ADA as well as the total number of doses received will also be provided.

Duration of ADA refers to the longevity of ADA and is defined as the time from the first on-study ADA-positive date to the first ADA-negative date after the last on-study ADA-positive date. Duration of ADA will be estimated by the Kaplan-Meier method. Patients who do not have an ADA-negative date after the last on-study ADA-positive date will be censored on the date of their last ADA-evaluable assessment. The median together with the corresponding 95% confidence interval (using log-log transformation method) and range (minimum, maximum) will be provided.

7.8.2 Evaluation of ADA

The following analyses will be conducted for anti-NKTR-214/anti-PEG, anti-IL-2 and anti-nivolumab, separately.

- Safety: All patients with ADA as mentioned above will be assessed for potential infusion related reactions under NKTR 214 safety events and will be compared against ADA negative patients, where infusion related reaction events that start after study drug administration on the same day or next day will be included.
- Efficacy: Objective response rate will be presented by ADA status.
- Concentration: Pre-dose NKTR-214 RC and pre-dose NKTR-214 AC concentrations will be summarized by ADA status.

7.8.3 Definitions

There are two sets of definitions: one for categorizing individual samples ([Table 4](#)) and another for categorizing patient responses ([Table 5](#)).

Table 4: ADA Status: Individual Samples

ADA Status	Definition
Baseline negative	ADA is not detected in the last sample before initiation of treatment
Baseline positive	ADA is detected in the last sample before initiation of treatment
Anti-NKTR-214 ADA-positive sample	After initiation of treatment, (1) an ADA detected (positive seroconversion) sample in a patient for whom anti-NKTR-214 ADA is not detected at baseline, or (2) an ADA detected sample with anti-NKTR-214 titer to be at least 4-fold or greater (\geq) than baseline positive titer
Anti-PEG ADA-positive sample	Sample with a positive result in PEG-immunocompetition assay.
Anti-IL-2 ADA-positive sample	After initiation of treatment, (1) an ADA detected (positive seroconversion) sample in a patient for whom anti-IL-2 ADA is not detected at baseline, or (2) an ADA detected sample with anti-IL-2 titer to be at least 4-fold or greater (\geq) than baseline positive titer
Anti-nivolumab ADA-positive sample	After initiation of treatment, (1) an ADA detected (positive seroconversion) sample in a patient for whom anti-Nivolumab ADA is not detected at baseline, or (2) an ADA detected sample with anti-nivolumab titer to be at least 4-fold or greater (\geq) than baseline positive titer
ADA-negative	After initiation of treatment, assay result is not a positive sample relative to baseline, i.e., increase from baseline is <4-fold

Table 5: ADA Response Categories: Patient Level

ADA status	Description
Baseline ADA-positive	A patient with baseline ADA-positive sample
ADA-negative patient	Patient with no ADA-positive sample after the initiation of treatment. Note: due to the definition of an ADA positive sample for a patient testing positive at baseline (see sample status table, above), it is possible (but highly unlikely) for a patient with a stable anti-drug titer throughout the study to be classified as 'ADA-negative'
ADA-positive patient (Treatment-emergent positive)	Patient with at least 1 ADA positive-sample (relative to baseline) at any time after initiation of treatment
Persistent positive	ADA-positive sample at 2 or more consecutive time points, where the first and last ADA-positive samples are at least 16 weeks apart (endogenous human IgG1, IgG2, and IgG4 have approximate half-lives in the range of 21-25 days, and 5 half-lives are approximately equal to 16 weeks)
Not PP-last sample positive	Not persistent positive with ADA-positive sample at the last sampling time point
Transiently positive or other positive	Patient not persistently positive but has 1 or more ADA positive samples with the last sample being ADA-negative.
Neutralizing positive	At least 1 ADA-positive sample with neutralizing antibodies detected

Abbreviation: PP = persistent positive

